### **7.7.3 AEs and Serious Adverse Events (SAEs)**

AEs will be tabulated using MedDRA preferred terms. The number and percentage of participants experiencing each specific AE (All AEs, Grade 2 or higher, and SAEs) will be tabulated by severity and by relationship to study product. For the calculations in these tables, each participant's AEs will be counted once as the maximum severity and relationship to study product. AEs leading to temporarily or permanently stopping drug will also be summarized. AEs will be summarized for those that are treatment emergent during LA dosing.

A listing of EAEs reported to the DAIDS RSC Safety Office will provide details of the events including severity, relationship to study product, time between onset and last injection, number of injections received, and a summary of the event.

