12.4 Proportion of injection visits that occurred “on-time”

Population: Injection population

Analysis description: Number and percent of injection visits (up to 5 per participant) that occur “on-time”¹, using the number of injections given as the denominator. This will be presented along with the total number and percent of injections given, among all intended injections (i.e. 5 injections per participant).

¹The target injection date is defined by the W5 visit i.e. for the initial injection, the target injection date is 0 days (same day), and is +28, +84, +140, +196 days from the W5 visit for injections 2-5, respectively. The target visit window for injection visits for the week 5 injection is 0 to 3 days after the W5 visit (if the injection could not be done on the same day as the W5 visit), for all other injection visits (W9, W17, W25, W33) the target window is +/-3 days from the target injection date. Injection dates happening within the target window are considered “on-time”.

12.5 Change from enrollment of self-reported sexual behavior (number of sexual partners, and number of episodes of anal intercourse without a condom) during the study period

Note: This secondary analysis will not be included in the Clinical Study Report.

Population: Enrolled population

Analysis description: Counts of sexual partners and episodes of anal intercourse without a condom will be summarized (mean and median) at enrollment and each regular Step 1 and Step 2 follow-up visit (W4, W5, W9, W17, W25, W33, +8).

12.6 Evaluate rates of HIV drug resistance among participants who acquire HIV infection during the study

Population: Seroconverter population

Analysis description: Data from steps 1, 2, and 3 will be included. The number of cases of drug resistance will be summarized. All cases of drug resistance among incident HIV infections will be described.

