Impact on Creatinine	CAB	Regulatory Interest, Therapeutic Area

Confidential

All proprietary rights reserved

Page 22 of 27

Hyperglycemia/new onset diabetes mellitus	CAB	Observation from 083, Class
---	-----	-----------------------------

Common ISR adverse events are defined by MedDRA preferred terms including injection site pain, injection site induration, injection site nodules and preferred terms of any other ISR exceeding the threshold as specified in the ADRG. ISRs will be explored regardless of IP relationship.

Each one of the AESIs described in Table 3 will be explored via the data listings in more detail. Listings will summarize Adverse events that occurred during Step 1 and/or Step 2 of the study and will contain information to assess the following.

Event Characteristics: The characteristics of all event occurrences during the post-baseline period will look at event characteristics (serious, drug-related, leading to withdrawal, or Grade 3/4, fatal), number of events per participant, outcome, maximum grade or intensity and action taken.

Time to First Event (TTFE) and Duration of Events: Time of onset and duration of event will be provided.

In addition, Pyrexia Plus includes PT: (Chills – 10008531, Feeling of Body Temperature Change - 10061458, Feeling Hot - 10016334, Body Temperature Increased - 10005911, Pyrexia - 10037660, Influenza Like Illness - 10022004, Fever – 10016558) events will be looked at in relation to timing of previous injection.

No formal summaries or statistical comparisons are planned for AESI.

15. APPENDIX B – Variable Definitions

1. CES-D-10 (score/categories)

Create a score based on 10 items below (in CASI questionnaire):

In the list below, please indicate how often you have felt this way during the past week by ticking the appropriate box for each question:

1. I was bothered by things that usually don't bother me.
2. I had trouble keeping my mind on what I was doing.
3. I felt depressed.
4. I felt that everything I did was an effort.
5. I felt hopeful about the future.
6. I felt fearful or afraid.
7. My sleep was restless.
8. I was happy.
9. I felt lonely.
10. I could not "get going", I did not feel motivated.

Scoring:

	Rarely or none of the time (less than 1 day)	Some or a little of the time (1-2 days)	Occasionally or a moderate amount of time (3-4 days)	All of the time (5-7 days)
--	--	---	--	----------------------------

Questions 5 & 8	3	2	1	0
All other questions	0	1	2	3

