(2) https://cdn.who.int/media/docs/default-source/child-growth/growth-reference-5-19-years/computation.pdf?sfvrsn=c2ff6a95_4

Age-specific values of necessary parameters $L(t)$, $M(t)$, and $S(t)$ can be downloaded from the website (1) (see section: “**Expanded tables for constructing national health cards**” link to dataset “**z-scores: girls**”)

Categorical BMI classification based on age-standardized BMI z-score as follows:

- Obesity: $>+2$
- Overweight: $>+1$ and $\leq+2$
- Normal: >-2 and $\leq+1$
- Thinness: >-3 and ≤-2
- Severe thinness: ≤-3

16. APPENDIX C – Imputation of missing dates

Missing Start and Stop Dates for Prior and Concomitant Medication, and Medical History

The Assumption is to consider the most conservative judgment when imputing.

Start date:

When imputing a start date ensure that the new imputed date is sensible i.e. is prior to the end date and the general rules are:

1. If start date is completely missing, start date will not be imputed
2. If year and month are present and day is missing, set day to the 1st day of month.
3. If year and day are present and month is missing, then set month to January.
4. If year is present and month and day are missing, set month and day to January 1st.

Stop date:

1. If end date is completely missing, end date will not be imputed
2. If year and month are present and day is missing, set day to the last day of month.
3. If year and day are present and month is missing, set month to December
4. If year is present and month and day are missing, set month and day to December 31st.

Missing Start and Stop Dates for Adverse Events (including ISRs)

The Assumption is to consider the most conservative judgment when imputing.

Start date:

1. If start date is completely missing, start date is set to date of first dose.
2. If (year is present, and month and day are missing) or (year and day are present, and month is missing):
 - a. If year = year of first dose, then set month and day to month and day of first dose.
 - b. If year < year of first dose, then set month and day to December 31st.
 - c. If year > year of first dose, then set month and day to January 1st.
3. If month and year are present and day is missing:
 - a. If year = year of first dose and
 - i. If month = month of first dose, then set day to day of first dose date.
 - ii. If month < month of first dose, then set day to last day of month.
 - iii. If month > month of first dose, then set day to 1st day of month.

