 - b. If year < year of first dose, then set day to last day of month.
 - c. If year > year of first dose, then set day to 1st day of month.

Stop date:

If the outcome of the AE was ongoing or unknown, then the rules outlined below will not be applied.

1. If stop date is completely missing, stop date is set to date of study discontinuation.
2. If (year is present, and month and day are missing) or (year and day are present, and month is missing):
 - a. If year = year of study discontinuation, then set month and day to month and day of study discontinuation.
 - b. If year < year of study discontinuation, then set month and day to December 31st.
 - c. If year > year of study discontinuation, then set month and day to December 31st.
3. If month and year are present and day is missing:
 - a. If year = year of study discontinuation and
 - i. If month = month of study discontinuation, then set day to day of study discontinuation date
 - ii. If month < month of study discontinuation, then set day to last day of month.
 - iii. If month > month of study discontinuation, then set day to last day of month.
 - b. If year < year of study discontinuation, then set day to last day of month.
 - c. If year > year of study discontinuation, then set day to last day of month.

Missing Start and Stop Dates for Protocol Deviations

The Assumption is to consider the most conservative judgment when imputing.

Start date:

When imputing a start date ensure that the new imputed date is sensible i.e. is prior to the end date and the general rules are:

1. If start date is completely missing, start date will not be imputed
2. If (year is present, and month and day are missing) or (year and day are present, and month is missing), set month and day to January 1st.
3. If year and month are present and day is missing, set day to the 1st day of month.

Stop date:

1. If end date is completely missing, end date will not be imputed
2. If (year is present, and month and day are missing) or (year and day are present, and month is missing), set month and day to December 31st.
3. If year and month are present and day is missing, set day to the last day of month.

Approved

Signature Page for SCHARP-TMF-32741 v2.0

Reason for signing: Approved	Name: [name] Role: Data Analytics Date of signature: 17-Jan-2023 19:54:18 GMT+0000
------------------------------	--

Reason for signing: Approved	Name: [name] Role: Hutch SDMC Date of signature: 17-Jan-2023 23:02:14 GMT+0000

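### For an ISR with only the onset day missing, SAP Appendix C ignores the injection given that month and usually dates a reaction to injections 2 to 5 before the injection that caused it

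*SAP*

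**What the plan says.** SAP section 16 (Appendix C) has a block headed "Missing Start and Stop Dates for Adverse Events (including ISRs", so ISRs are expressly in scope. Start-date rule 3 covers events with month and year known and the day missing. Three of its branches matter here:

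- Same month and year as first dose (3.a.i): "If month = month of first dose, then set day to day of first dose date".
- Same year, later month (3.a.iii): "If month > month of first dose, then set day to 1st day of month".
- Later year (3.c): "If year > year of first dose, then set day to 1st day of month".

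No branch refers to any injection after first dose. The appendix does not say whether first dose is the oral CAB dose at enrollment or the first injection.

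SAP 12.4 puts the target dates of injections 2 to 5 at "28, +84, +140, +196 days from the W5 visit for injections 2-5, respectively", and "the target window is +/-3 days from the target injection date".

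Onset timing is used in two places. SAP Appendix A lists time of onset and duration for each adverse event of special interest (AESI), ISRs among them, and says that Pyrexia Plus "events will be looked at in relation to timing of previous injection". Protocol 7.7.3 plans a listing of expedited adverse events (EAEs) that includes "time between onset and last injection, number of injections received, and a summary of the event".

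**The concern.** An ISR cannot begin before the injection that caused it, yet the rule as written produces such dates. Suppose injection 3 is given on 15 March and an ISR is recorded as March, day unknown. Rule 3 sets onset to 1 March, 14 days before the injection. Injection 2 was due 84 - 28 = 56 days before injection 3, so the listing would show a reaction 56 - 14 = 42 days after injection 2.

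An acute reaction then reads as a late one after the wrong injection, and its duration is lengthened. If the stop day is also missing, and March is not the month of study discontinuation, the stop rule gives 31 March. A reaction of a few days is then listed as lasting the whole month. Protocol 6.3 gives a median of about 5 days for injection-site pain.

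For injection 1 the stake can be higher. If first dose is the oral dose, the imputed onset can fall before the primary safety window in SAP 8.1 opens.

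**Working it through.** The documents state no share of misdated events, so there is no planned figure to reproduce.

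**Inputs from the documents.** Rule 3 as above; injections 2 to 5 at +28, +84, +140 and +196 days from the Week 5 visit (SAP 12.4); oral CAB for five weeks, so the first oral dose is 35 days before injection 1 (Protocol 4.1); nine participants enrolled (SAP 6.4).

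**Assumptions.** Injection dates are uniform over a four-year calendar cycle (1461 days, 48 month starts). The lag L from injection to onset is fixed at 0 to 7 days. The documents give no lag; seven days is the interval to the safety visit at which ISRs are evaluated (Protocol 5.6 and Appendix II).

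**Injections 2 to 5.** The imputed onset is not before the injection in two cases: the injection falls on the 1st of a month (48 days in 1461), or true onset crosses into the next month (48 × L days in 1461). Hence

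share imputed before the injection = 1 - (L + 1) × 48 / 1461.

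| L (days) | (L + 1) × 48 | Share before injection |
|---|---|---|
| 0 | 48 | 96.7% |
| 1 | 96 | 93.4% |
| 2 | 144 | 90.1% |
| 3 | 192 | 86.9% |
| 4 | 240 | 83.6% |
| 5 | 288 | 80.3% |
| 6 | 336 | 77.0% |
| 7 | 384 | 73.7% |

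The equal-weight average is 93.4% over lags 0-2 and 85.2% over lags 0-7. Running rule 3 literally over all 1461 Week 5 dates gives the same figures for both meanings of first dose, with and without the ±3-day window.

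**Injections 1 and 2 in one month.** If first dose is the first injection, 3.a.i applies and sets onset to the date of injection 1, still before injection 2. So 3.a.i does not rescue these cases.

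**Injection 1.** If first dose is the first injection, 3.a.i returns the injection date and 0% are misplaced. If it is the oral dose, injection 1 comes 35 days later. No month is longer than 31 days, so it is always in a later month, and the shares in the table apply. The imputed 1st then lies between enrollment and Week 5: outside the SAP 8.1 window and inside the oral-phase analysis of SAP 12.2.

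**Primary endpoint for injections 2 to 5.** The SAP 8.1 window opens at the first injection visit, and each participant counts once. Moving an onset within the window changes nothing. An onset can leave the window only if first dose is oral, injections 1 and 2 share a month, and injection 1 is not on the 1st. That needs injection 1 on day 2 or 3 of a 31-day month or day 2 of a 30-day month: (28 × 2 + 16 × 1) / 1461 = 72 / 1461 = 4.9% of start dates at most, and for injection 2 only.

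**Scale.** Nine participants × 4 injections = at most 36 injections numbered 2 to 5.

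**The case against.** The best case on the other side is that little depends on this. AESIs are handled through listings, and Appendix A plans no formal summaries or comparisons for them. The EAE listing also carries a narrative. ISRs are evaluated one week after every Step 2 injection, and data queries are routine, so a missing day for an acute reaction may be uncommon. No affected event is shown. All of this stands and limits the weight of the point; it does not make the imputed dates possible.

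Several stronger readings are tempting and are not supported:

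- **A single share of about 93%.** It needs a lag of one day, or one uniform on 0-2 days, and the documents give neither.
- **Misattribution of ISRs by successive injection.** Protocol 7.7.2 does not say that ISRs are assigned to injections by onset date. Assignment by evaluation visit is at least as natural.
- **A missing safeguard that the other blocks have.** The medication and deviation rules ask for a sensible imputed date, but explain this only as start before end. A date of 1 March passes that test, so copying it would cure nothing.
- **The same error for every adverse event.** A fever or headache in an injection month may truly have begun before the injection. Only for ISRs is the imputed date impossible.

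**Conclusion.** The concern holds for ISRs with the day missing. For injections 2 to 5, rule 3 usually dates onset before the causing injection under either meaning of first dose: about 90-97% of such events for lags of 0-2 days and 74-97% for lags of 0-7 days, given evenly spread injection dates. The lag and the spread are assumptions; the mechanism follows from the rule itself.

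The consequence for these injections is wrong time of onset and duration in the AESI listings and, where the event is an EAE, wrong time from last injection. A reader might infer that the primary safety result is biased; for injections 2 to 5 it essentially is not.

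Injection 1 depends on the undefined anchor. Protocol 5.2 uses the term first dose for oral CAB at enrollment, which makes the oral reading plausible. Under it, a Grade 2 or higher ISR could drop out of the primary analysis. If all nine participants were injected, one participant is 1/9 = 11.1 percentage points, and the estimate moves only if that participant has no other qualifying event in the window.

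How many events lack a day is unknown.

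**What to change.** In Appendix C, add an override of start-date rule 3 for ISRs, including 3.a.i: set a day-missing onset to the later of (a) the 1st of the recorded month and (b) the date of the most recent injection before the visit at which the ISR was reported. If that injection falls after the recorded month because the report came late, step back to the last injection on or before the end of that month.

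This handles the awkward cases. With injection 3 on 15 March, a March ISR is dated 15 March. With an injection on 30 January and onset recorded as February, reported a week after the injection, the date is 1 February, which is after the injection. With injections 1 and 2 in the same month, the reporting visit decides between them. No ISR onset then precedes its injection, whichever meaning of first dose is adopted.

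Leave rule 3 as it is for other adverse events. Flag imputed onset dates in the Pyrexia Plus, AESI and EAE listings, so that a reader does not take an interval from last injection as observed.

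The cost is a few lines in Appendix C and in the date-imputation code. Nothing changes if no ISR has a missing day.
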